6 STUDY INTERVENTION

6.1 STUDY INTERVENTION

- Potential participants (parents + child) who meet the initial inclusion and exclusion criteria can participate in this trial
- If participants meet the inclusion and exclusion criteria after the parents have signed the informed consent, participants will begin the trial.
- The parents will complete the Baseline questionnaire and provide the Baseline height and weight measurements of the children. The children will complete the Baseline cognitive assessments.
- After the baseline data collection, participants will be randomly allocated into the intervention or placebo study group. The participants and Citruslabs will not be informed who is in the intervention or the placebo group.
- The children will take 1 one scoop of the powder mixed with 6-8 oz of water, milk, or smoothies every morning.
- Parents will complete questionnaires at the end of Month 1, Month 2, Month 3, Month 4, Month 5, and Month 6.
- Parents will provide height and weight measurements of the children at Month 2, Month 4 and Month 6.
- The children will repeat the cognitive assessments at the end of Month 6.
- Completion of the Month 6 measurements marks the end of the study.

6.2 INTERVENTION FORMULATION

Intervention Product: Protein, Vitamin A, Vitamin C, Vitamin D, Vitamin E, Thiamine, Riboflavin, Niacin, Vitamin B6, Folate, Vitamin B12, Biotin, Pantothenic Acid, Choline, Calcium, Iron, Phosphorus, Iodine, Magnesium, Zinc, Selenium, Copper, Chloride, Sodium, Potassium, Organic Flax Seed Powder, L-Taurine, Inositol Hexanicotinate, L-Arginine, Bacillus subtilis DE111® Complex (1 Billion CFU) (Probiotic), Eucommia Bark Extract, Vitamin K, Whey Protein Concentrate, Chocolate Bean Powder Processed with Alkali, Organic Evaporated Cane Sugar, Milk Protein Concentrate, Guar Gum Powder, Natural Flavor, Potassium Chloride, Silicon Dioxide, Rebaudioside A (from Stevia Leaf Extract), Sucralose.

Placebo Product Ingredients: Maltodextrin, Guar gum powder, Silicon dioxide, Cocoa powder, Natural creamy vanilla flavor, Organic evaporated cane sugar, Stevia leaf extract, and Sucralose.

6.3 RANDOMIZATION AND BLINDING

Participants will be randomized into the intervention group (NuBest Tall Growth Protein Powder) or into a placebo product control group. Randomization occurs via a randomization tool that will equally place participants into a group that will use product A or B. The research coordinator who will conduct the randomization will not know which product is the test product and which is the control.

This study will be double-blinded; the study participants and study coordinators will be blinded to the intervention or product allocation. Only the sponsor will know which product, A or B, contains the active ingredients. After the study is complete, the allocation will be unblinded prior to the analysis. Both groups will receive products that look identical.

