1.1 SYNOPSIS

Title:	A Randomized, Double-blind, Placebo-controlled Study to Evaluate the Effects of a Dietary Supplement on Children's Health Outcomes
	This is a virtual, two-armed, randomized, double-blinded, placebo- controlled clinical trial that will last 6 months. Participants will take the NuBest Tall Growth Protein Powder or a placebo product daily.
Study Description:	The children's parents will complete questionnaires at baseline and regularly during the study period (Month 1, Month 2, Month 3, Month 4, Month 5, and Month 6).
	The children will complete cognitive assessments at home at Baseline and Month 6 (Endline).
	Parents will also provide height and weight measurements of the children at Baseline, Month 2, Month 4, and Month 6.
	Primary Objective: To examine the effect of the NuBest Tall Growth Protein Powder on cognitive function.
Objectives:	Secondary Objective: To investigate the impact of the NuBest Tall Growth Protein Powder on a range of health parameters, including height, weight, energy levels, immune function, and digestion.
	Primary Endpoint: The primary endpoint of this study is an improvement in cognitive function. Cognitive battery testing scores will be compared across the trial measurement points.
Endpoints:	Secondary Endpoints: The secondary endpoint is an increase in a range of parameters associated with health, including height, weight, energy levels, immune function, and digestion. Parents will provide height and weight measurements for the children and will complete questionnaires evaluating other health outcomes.
Study Population:	This study will recruit 60 participants (60 pairs of parents + child). The parents may be of any age group, the children must be aged as follows: Boys: 12 to 16 years Girls: 10 to 14 years
	Arm 1: Intervention - 30 participants

	Arm 2: Placebo - 30 participants		
Description of Sites/Facilities Enrolling Participants:	Virtual		

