3 OBJECTIVES AND ENDPOINTS

OBJECTIVES	ENDPOINTS	TIMEPOINTS	ASSESSED BY	JUSTIFICATION FOR ENDPOINTS
Primary				
To examine the effect of the NuBest Tall Growth Protein Powder cognitive function.	Improvement in score on assessments: • Double Trouble • Feature Match • Grammatical Reasoning • Digit Span • Token Search	Baseline and Month 6	Cognitive Battery Testing	The combination of these cognitive assessments will provide objective data on the efficacy of the product in improving specific domains of cognitive function.
Secondary				
	Increase in height			

	Maintenance of a healthy weight	Baseline, Month 2, Month 4, Month 6 (height & weight measurements)	Height measured using an Ultrasonic Height	
To investigate the impact of the NuBest Tall Growth Protein Powder on a range of health parameters, including height, weight, energy levels, immune function, and digestion.	Increase energy levels		Measuring Stadiometer	The combination of objective measurements and questionnaires will provide both independent and participant perception data on secondary health parameters.
	Improved signs of digestive health		Weight measured using a FitBit Smart Scale.	
	Increased immune	Baseline, Month 1, Month 2, Month 3, Month 4, Month 5, Month 6.		
	function (assessed via the number of times the child has been ill in the past 6 months)		Study-specific questionnaires	

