5 STUDY POPULATION

5.1 INCLUSION CRITERIA

To be eligible to participate in this study, an individual must meet all of the following criteria:

- 1. A parent of a child within the following age ranges:
 - Boy: 12 to 16 years
 - Girl: 10 to 14 years
- 2. Interested in their child trialing a dietary supplement designed to improve overall health outcomes in children, including height, maintenance of a healthy weight, cognitive function, immune function, and energy levels.
- 3. Willing to refrain from giving their child any vitamins, minerals, or herbal supplements of any kind for the duration of the study
- 4. Parents willing to weigh and measure the height of their child throughout the study
- 5. Generally healthy do not have any uncontrolled chronic disease

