5.4 JUSTIFICATION OF SAMPLE SIZE

60 participants, 30 each in the intervention and placebo arms, is sufficient to establish differences between the two study conditions. This will allow for meaningful between-group comparisons to adequately assess the efficacy of the test product versus placebo control.

[figure not shown]

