7 STATISTICAL CONSIDERATIONS

Following data collection and the completion of the trial, the data will be analyzed by Citruslabs to determine the effect of the intervention versus the placebo. Between-arm and participant repeated measures between time point statistical tests will be used to examine differences in health outcomes during the study and compared to the placebo. Percentages of people who experienced improvements will also be examined. The analysis will adopt an intent-to-treat (ITT) approach, reflecting the primary objective of assessing the effectiveness of the test product as it would be used in the general population, inclusive of all randomized participants, irrespective of adherence or protocol deviations.

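### Eligibility ties sex to age, but the plan specifies neither stratification by sex nor adjustment for sex, age or baseline value, which gives up some precision that is cheap to keep

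*Combined protocol and SAP*

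**What the plan says.** Section 5.1 of the combined protocol and SAP sets eligibility by sex: "Boy: 12 to 16 years" and "Girl: 10 to 14 years". The synopsis (Section 1.1) gives the same ranges. They are offset by two years and overlap only from 12 to 14.

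Section 6.3 gives the allocation method in one sentence: "Randomization occurs via a randomization tool that will equally place participants into a group that will use product A or B". It names no stratification factor, block size or minimization variable. Section 5.4 fixes 30 children per arm.

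Section 3 lists the primary endpoint as "Improvement in score on assessments" for five cognitive tests, measured at Baseline and Month 6. Among the secondary endpoints is "Increase in height". No age- or sex-standardised scoring is stated for either.

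Section 7 describes the analysis as follows: "Between-arm and participant repeated measures between time point statistical tests will be used to examine differences in health outcomes". It names no model and no covariate.

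Sex and age must be known to judge eligibility. Section 6.1 places the baseline questionnaire, height, weight and cognitive tests before allocation.

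**The concern.** The eligibility rule makes sex a marker of age. If an arm receives more boys by chance, it will also tend to be older, and the two differences act together. The participants are growing adolescents, and three of the five cognitive tests are timed. Six-month growth or six-month gain in score could plausibly depend on age or sex. If it does, part of an observed arm difference would reflect who was allocated where. Variation between the sexes would also sit in the residual error of an unadjusted comparison.

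The design and the analysis could each deal with this, and the plan provides for neither. With 30 per arm there is little precision to spare: at an assumed two-sided alpha of 0.05, the effect detectable with 80% power is 0.72 SD, and power at 0.5 SD is 49%.

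**Working it through.** **No plan figure to reproduce.** Section 5.4 states that "60 participants, 30 each in the intervention and placebo arms, is sufficient to establish differences between the two study conditions" but gives no alpha, power, effect size, SD or dropout rate. The check below therefore concerns the imbalance itself.

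**Inputs from the documents.** 60 children, 30 per arm (Section 5.4); boys 12 to 16 and girls 10 to 14 (Section 5.1), with mid-range ages of 14 and 12.

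**Assumptions not in the documents.** 30 boys among 60, with 20 and 40 as alternatives; a two-year gap in mean age between the sexes; ages uniform within each sex over 4 years, or 5 years if the upper limit is a completed year; a boy-girl difference on the outcome of 0.2, 0.5 or 0.8 within-sex SD.

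**1. Chance of a sex imbalance.** With allocation fixed at 30:30 and no stratification, the number of boys in one arm is hypergeometric (60 children, B boys, 30 drawn). If it is X, the arms differ by |2X − B| boys.

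| Boys in total | differ by ≥4 | differ by ≥6 | differ by ≥8 |
|---|---|---|---|
| 30 | 44% | 20% | 7% |
| 20 or 40 | 41% | 17% | 5% |

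**2. Age carried by the sex imbalance.** The mean-age difference is (difference in boys ÷ 30) × 2 years. For 4, 6 and 8 boys this is 0.27, 0.40 and 0.53 years. The 18 against 12 case is 6/30 × 2 = 0.40.

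**3. Shift in an unadjusted contrast at 18 against 12.** The shift is g × 6/30, where g is the boy-girl difference on the outcome. For g = 0.2, 0.5 and 0.8 it is 0.04, 0.10 and 0.16 SD. Against a standard error of √(2/30) = 0.258 SD, these are 0.15, 0.39 and 0.62 standard errors.

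**4. False-positive rate in such a sample.** With no product effect and the standard error held at 0.258, the two-sided rejection rate would be 5.3%, 6.7% and 9.5%. These are upper figures, because an unadjusted test also carries the between-sex variance in its standard error. At 60:40 that multiplies the standard error by √(1 + 0.24g²) = 1.005, 1.030 and 1.074. With the critical value 1.96 raised by those factors, the rates are about 5.2%, 6.0% and 7.2%.

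**5. Precision averaged over allocations.** With a 1:1 sex mix, unadjusted variance is 1 + g²/4 in within-sex units. Adjusting for sex multiplies the standard error by 1/√(1 + g²/4) = 0.995, 0.970 and 0.928. The reductions are about 0.5%, 3% and 7%.

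**6. What stratifying by sex does for age.** With 30 boys and 30 girls, the variance of age between the sexes is 1 (two means, each one year from the overall mean). Within sex it is 16/12 = 1.33 or 25/12 = 2.08. Stratification removes the between-sex share of the variance in the age imbalance: 1/2.33 = 43% or 1/3.08 = 32%. In simulation (40,000 runs per setting, with 20, 30 or 40 boys), the chance of a mean-age difference above 0.5 year fell from 19–21% to 9% with 4-year ranges, and from 26–27% to about 18% with 5-year ranges. Most of the age imbalance arises within sex and remains.

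**The case against.** The strongest reply is that unstratified 1:1 randomization is valid. Over all allocations the type I error is held, and the ordinary standard error of an unadjusted comparison already allows for chance sex imbalance. A reader might infer that the trial is biased by design; the documents do not support that. Steps 3 and 5 describe one loss of precision seen in two ways, conditionally and on average, and they should not be added together.

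A reader might also infer that the tool disregards sex, or that the sponsor has chosen an unadjusted analysis. Neither is stated. Section 6.3 does not describe the algorithm and Section 7 names no model. What can be said is that stratification and covariates are not specified.

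Nor is it shown that the primary result would be distorted. The cognitive and height endpoints are changes from baseline, so differences in level between younger and older children largely cancel. What is left is any dependence of the six-month change on sex or age, and the documents give no figure for that. This objection stands and limits the claim. It does not remove it, because Section 7 does not commit to a change-score test, and change scores do not remove differences in rate of gain.

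Finally, stratifying by sex leaves most of the age imbalance in place. That is right, and it is why adjustment in the analysis comes first in the fix.

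**Conclusion.** The point holds as a cheap gain in precision that the plan passes over. Its eligibility rule links sex to age, and neither the allocation text nor the analysis text deals with the link. If 30 of 60 children are boys, about one trial in five would have arms differing by 6 or more boys, with a mean-age difference of about 0.4 years or more from that source alone.

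The consequence is modest. Over the assumed range of 0.2 to 0.8 SD between the sexes, a split of 18 against 12 moves an unadjusted contrast by 0.04 to 0.16 SD, well below the 0.72 SD detectable at 80% power. The average gain from adjusting for sex is about 0.5 to 7% of the standard error. Gains from adding age and the baseline value depend on correlations that the documents do not give. The effect on the primary cognitive change is unknown for the same reason. No conclusion of the trial is invalidated by this point.

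**What to change.** In Section 7, prespecify the between-arm comparison as a model adjusted for the baseline value of the outcome, sex and age. ANCOVA at Month 6 would suit each cognitive test. A repeated-measures model with the same covariates would suit height and weight at Months 2, 4 and 6. This is the main change. It can be made even if enrolment has begun, provided it is fixed before the allocation is unblinded.

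In Section 6.3, if enrolment has not begun, set the tool to permuted blocks stratified by sex and say so. Two strata are workable with 60 children. If the tool already stratifies, one sentence stating that settles this part.

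The cost is one tool setting and about three degrees of freedom per model. No new data or visits are needed, since all three covariates are known before allocation.

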8.4 DATA COLLECTION AND MANAGEMENT RESPONSIBILITIES

Data collection is the responsibility of Citruslabs, which is responsible for ensuring the accuracy, completeness, legibility, and timeliness of the data reported.

Trial data will be entered into a 21 CFR Part 11-compliant data capture system provided by Citruslabs. The data system includes password protection and internal quality checks, such as automatic range checks, to identify data that appear inconsistent, incomplete, or inaccurate. Clinical data will be entered directly from the source documents.

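### Sections 3 and 7 leave open the primary test and the rule for five cognitive scores, and Section 6.3 lets that choice be made after unblinding

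*Combined protocol and SAP*

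**What the plan says.** - **Endpoint.** Section 3 lists Double Trouble, Feature Match, Grammatical Reasoning, Digit Span and Token Search under a single primary objective, measured at Baseline and Month 6. Its justification opens by referring to the assessments in combination, but closes by promising "objective data on the efficacy of the product in improving specific domains of cognitive function". It defines no composite and no any-score or all-scores rule.
- **Analysis.** Section 7 says "Between-arm and participant repeated measures between time point statistical tests will be used" and adds "Percentages of people who experienced improvements will also be examined". The population is intention-to-treat, "inclusive of all randomized participants, irrespective of adherence or protocol deviations". No specific test, model, significance level, primary contrast or multiplicity rule is given.
- **Contrast.** The synopsis speaks of comparing cognitive scores across measurement points. Section 5.4 says of the sample size: "This will allow for meaningful between-group comparisons".
- **Unblinding.** Section 6.3 says "After the study is complete, the allocation will be unblinded prior to the analysis". Section 6.1 says "Completion of the Month 6 measurements marks the end of the study".
- **Data handling.** Section 8.4 makes the trial administrator "responsible for ensuring the accuracy, completeness, legibility, and timeliness of the data reported" and describes automatic checks. It gives no rule for settling flagged records and no timing relative to release of the code. Under Sections 7 and 8.7 the same organisation analyses the data.

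**The concern.** Five scores and no decision rule leave several primary conclusions compatible with the same plan: one claim about overall cognition, five separate domain claims, or a claim from whichever score reaches significance. The false-positive rate and the meaning of a positive result differ widely between them.

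The order of events adds to this. Since no step is required between the end of data collection and release of the code, the rule and the test could be written down by someone who already knows which arm received the product. A reader of the results could not then tell a planned finding from a selected one. This matters here because Section 4.3 says the study is meant to help support marketing claims and Section 8.7 acknowledges the sponsor's financial interest.

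**Working it through.** **The plan's own figure.** The only design figure is 30 + 30 = 60. It cannot be reproduced, because the text gives no significance level, power, effect size or standard deviation.

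**Inputs.** From the documents: five primary scores, two time points, 30 per arm. Assumed: two-sided 0.05 per test, normal scores, baseline-to-Month 6 correlation r = 0.6 (range 0.4-0.8), between-test correlation ρ = 0.4 (range 0.2-0.6).

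**Step 1: closed-form bounds with no true effect.** If the five tests were independent, the chance of at least one significant score is 1 − 0.95^5 = 0.226. The upper bound is 5 × 0.05 = 0.25. With correlated test statistics it falls to 0.21, 0.18 and 0.15 at correlations of 0.3, 0.5 and 0.7.

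**Step 2: simulation of baseline-adjusted comparisons (ANCOVA) with no true effect.** The first five rows used 20,000 trials at each of nine correlation pairs (r = 0.4, 0.6, 0.8 by ρ = 0.2, 0.4, 0.6). The last row used 4,000 trials per setting at ρ = 0.2, 0.4, 0.6.

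| Decision rule | False-positive rate |
|---|---|
| Any of five unadjusted, either direction | 16.8-22.1% (about 20% at central values) |
| Any of five unadjusted, favouring the product | 8.2-11.3% (about 10%) |
| One fixed score | 4.8-5.4% |
| One standardised composite | 4.9-5.4% |
| Holm across five, at least one significant | 3.9-4.8% (about 4.5%) |
| All five favouring the product | 0.03% or less |

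The Holm row agrees with the closed form: a first rejection needs p < 0.01, and 1 − 0.99^5 = 0.049 under independence.

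**Step 3: what each remedy costs in power.** Effects are assumed, in SD of a single score. The figures come from 8,000 trials per setting and count only results favouring the product.

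| Assumed effect | One test, unadjusted | Holm | Composite |
|---|---|---|---|
| One test shifted 0.6 SD | 81% (69-96%) | 59% (44-88%) | 11% (8-23%) |
| All five shifted 0.4 SD | not computed | 59% (41-90%), at least one test | 74% (51-99%) |

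Normal-approximation check at central values, with √(30/2) = 3.873 and √(1 − 0.6²) = 0.8:

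- One test, unadjusted: 0.6/0.8 × 3.873 = 2.905, and Φ(2.905 − 1.960) = 0.83.
- Same test at 0.01: Φ(2.905 − 2.576) = 0.63.
- SD of the mean of five scores: √((1 + 4 × 0.4)/5) = 0.721.
- Composite, one test shifted: the mean moves 0.6/5 = 0.12; 0.12/0.721/0.8 × 3.873 = 0.806, and Φ(0.806 − 1.960) = 0.12.
- Composite, all five shifted 0.4: 0.4/0.721/0.8 × 3.873 = 2.686, and Φ(2.686 − 1.960) = 0.77.

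Each sits slightly above its simulated value, as expected when a normal approximation replaces the t distribution.

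**Step 4: the sequence of events.** Section 6.1 fixes when the study ends, and Section 6.3 places unblinding somewhere between that point and the analysis. Cleaning, a lock and sign-off could all fit in that window, but no supplied section requires any of them.

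**The case against.** The strongest reply is that the error inflation has nothing to do with unblinding. That stands: the same 17-22% would arise in a fully blinded analysis with the same open rule. Breaking the code before analysis is common and not a fault once data and methods are fixed. The defect therefore lies in Sections 3 and 7, and Section 6.3 only aggravates it.

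Second, the plan states no any-score rule. That also stands. A reader might infer that the trial has a 20% false-positive rate, but the documents do not support this. That rate belongs to one permissible reading, and the strictest reading gives almost zero. The finding is that the rule has not been chosen.

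Third, the reference in Section 3 to the assessments in combination could be read as a composite. It supports a joint reading, but it is endpoint justification: it gives no scoring or weighting, and the same sentence turns to separate domains.

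Fourth, safeguards exist: intention-to-treat analysis of everyone randomised, and analysis by a third party described as independent. They settle who is analysed and who analyses, but not which score or test carries the conclusion.

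Finally, Section 8.5 mentions a Manual of Procedures that was not supplied. A lock or a separate analysis plan may exist there, so the absence claimed here covers the supplied text only.

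**Conclusion.** The concern holds as a gap in Sections 3 and 7 that should be closed before the code is broken. Across decision rules that fit the text, the chance of a false primary claim runs from almost 0% (all five scores) to about 20% (any one unadjusted score, range 17-22%, or 8-11% in the product's favour). A single composite would hold it near 5% and Holm at about 4.5%. All of these rest on the assumed significance level and correlations; they show the size of the risk and are not figures from the documents.

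Two stronger readings should be avoided. One is that a within-arm comparison is the planned primary. The synopsis leaves room for it, but Sections 5.4 and 7 strongly imply a between-arm contrast; what is missing is a statement that it is primary. The other is that the code is broken as soon as Month 6 data are in. Section 6.3 gives a window, not a trigger, so the supportable claim is only that no lock or signed methods are required within it.

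**What to change.** 1. **Sections 3 and 7.** Name the between-arm comparison at Month 6, adjusted for the baseline score, as the primary analysis, and state the model. If the intended claim is overall cognitive function, analyse one standardised composite of the five scores. If claims are to be made per domain, apply Holm across the five. Label within-arm tests and improver percentages as supportive.
2. **Section 6.3.** State that cleaning decisions are made and recorded without the A/B code, the database is locked, and a dated analysis plan is signed before the allocation is unblinded. State that analyses devised later are exploratory. If a plan or lock procedure already exists elsewhere, cite it here by date.

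Changing Section 6.3 alone would leave the primary conclusion undefined.

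The cost is some writing and a short delay before unblinding, with no new data or participants. The choice also has a power cost, shown in the second table. A composite suits an effect spread over all five tests but would largely miss one confined to a single test; Holm loses less in that case and gives less power than the composite when the effect is broad. The sponsor should decide from the intended claim, before the code is released.
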